For patients who are being treated beyond progression, CT scans (PET is optional) should be performed every 3 months as long as treatment is ongoing and 4-6 weeks after the last dose of atezolizumab. Thereafter, patients will undergo CT scans every 6 months.

22.6 Appendix 6

Anaphylaxis Precautions

Equipment Needed

Tourniquet

Oxygen

Epinephrine for subcutaneous, intravenous and/or endotracheal use in accordance with standard practice

Antihistamines

Corticosteroids

Intravenous infusion solutions, tubing, catheters, and tape

Procedures

In the event of a suspected anaphylactic reaction during study drug infusion, the following procedures should be performed:

1. Stop the study drug infusion.
2. Apply a tourniquet proximal to the injection site to slow systemic absorption of study drug. Do not obstruct arterial flow in the limb.
3. Maintain an adequate airway.
4. Administer antihistamines, epinephrine, or other medications as required by patient status and directed by the physician in charge.
5. Continue to observe the patient and document observation.

22.7 Appendix 7
Safety Reporting Fax Cover Sheet

A Member of the Roche Group

GENENTECH SUPPORTED RESEARCH

AE/SAE [contact]

Alternate [contact]

Page 1 of ____

| | |
|--|---------------------------------------|
| Genentech Study Number | |
| Principal Investigator | |
| Site Name | |
| Reporter name | |
| Reporter Telephone # | |
| Reporter Fax # | |
| Initial Report Date | ____ / ____ / ____ dd / mmm / yyyy |
| Follow-up Report Date | ____ / ____ / ____ dd / mmm / yyyy |
| Patient Initials (Please enter a dash if the patient has no middle name) | ____ - ____ - ____ |

SAE or Safety Reporting questions, contact Genentech Safety: [contact]

PLEASE PLACE FDA MEDWATCH 3500 Form or SAFETY REPORT BEHIND THIS COVER SHEET.

22. 8 Appendix 8

Management Of Toxicities Associated With Atezolizumab

To date, the following adverse events are identified risks associated with atezolizumab: dermatologic reactions, hepatitis, hypothyroidism, pneumonitis, influenza-like illness, and IRRs. Potential risks associated with atezolizumab include colitis, endocrine disorders, hypersensitivity, neurologic disorders, pericardial effusions, eye toxicity, and development of anti-therapeutic antibodies. Detailed information is provided below for the following risks: GI toxicity, hepatotoxicity, dermatologic toxicity, hypothyroidism, pulmonary toxicity, influenza-like illness, systemic immune activation (SIA), pancreatic toxicity, pericardial effusions, eye toxicity, and IRRs.

Gastrointestinal Toxicity

Immune-related colitis has been associated with the administration of atezolizumab and is an identified risk for atezolizumab.

Patients should be advised to inform the investigator if any event of diarrhea occurs, even if it is mild. Suspected colitis should be further evaluated, and infectious or alternative etiologies should be ruled out.

If the event is of significant duration (>5 days) or is associated with signs of systemic inflammation or acute phase reactants (e.g., increased C-reactive protein or platelet count or bandemia), it is recommended to do the following:

Perform sigmoidoscopy (or colonoscopy, if appropriate) with colonic biopsy, with three to five specimens for standard paraffin block to check for inflammation and lymphocytic infiltrates to confirm diagnosis of colitis. If possible, one or two biopsy specimens should be snap frozen and stored.

Perform laboratory tests to rule out alternative etiology (i.e., WBCs and stool calprotectin).

Hepatotoxicity

Immune-related hepatitis has been associated with the administration of atezolizumab. Hepatitis is an identified risk for atezolizumab.

Eligible patients must have adequate liver function, as manifested by measurements of total bilirubin and hepatic transaminases, and liver function will be monitored throughout study treatment.

Patients presenting with right upper-quadrant abdominal pain and/or unexplained nausea or vomiting should have hepatic enzyme tests performed immediately, and results should be reviewed before administration of the next dose of study treatment.

If hepatic enzymes become elevated, neoplastic, concurrent medication, viral hepatitis, and toxic etiologies should be considered and addressed, as appropriate. Imaging of the liver, gall bladder, and biliary tree should be performed to rule out neoplastic or other causes for the hepatic enzyme elevations. Anti-nuclear antibody, perinuclear anti-neutrophil cytoplasmic antibody, anti-liver kidney microsome antibodies, and anti-smooth muscle antibody tests should be performed if an autoimmune etiology is considered.

Dermatologic Toxicity

Treatment-emergent rash has been associated with atezolizumab. The majority of the cases of rash were mild in severity and self-limited, with or without pruritus. Dermatologic reactions are an identified risk for atezolizumab. A dermatologist should evaluate persistent and/or severe rash or pruritus. A biopsy should be considered unless contraindicated.

Hypothyroidism

Hypothyroidism has been associated with the administration of atezolizumab and is an identified risk for atezolizumab. Patients with unexplained symptoms such as fatigue, myalgia, impotence, mental status change, or constipation should be investigated for the presence of thyroid, pituitary, or adrenal endocrinopathy, as well as for hyponatremia or hyperkalemia. An endocrinologist should be consulted if an endocrinopathy is suspected. TSH and free T4 levels should be evaluated to determine whether thyroid abnormalities are present. TSH, prolactin, and morning cortisol levels will help to differentiate primary adrenal insufficiency from primary pituitary insufficiency.

Pulmonary Toxicity

Dyspnea, cough, fatigue, hypoxia, and pulmonary infiltrates have been associated with the administration of atezolizumab and have primarily been observed in patients with underlying NSCLC. Pneumonitis is an identified risk for atezolizumab. Mild to moderate events of pneumonitis have been reported with atezolizumab. All pulmonary events should be thoroughly evaluated for other commonly reported etiologies, such as pneumonia/infection, lymphangitic carcinomatosis, pulmonary embolism, heart failure, chronic obstructive pulmonary disease, or pulmonary hypertension, as outlined below:

- Measurement of oxygen saturation (i.e., arterial blood gas)
- High-resolution CT scan of the chest
- Bronchoscopy with bronchoalveolar lavage and biopsy
- Pulmonary function tests (including diffusion capacity of the lung carbon monoxide)
- Pulmonary function testing with a pulmonary embolism protocol

Patients will be assessed for pulmonary signs and symptoms throughout the study. Patients will also have CT scans of the chest at every tumor assessment.

Influenza-Like Illness

Influenza-like illness has been reported in patients receiving atezolizumab as a single agent and in combination with vemurafenib, bevacizumab, or platinum doublet therapy. Symptoms have included fever, fatigue, asthenia, chills, myalgia, arthralgia, and headache. Symptoms have occurred alone or concurrently. Influenza-like illness has been observed primarily 1-2 weeks after the first treatment cycle. The events have been mild to moderate in severity.

Systemic Immune Activation

SIA is a rare condition characterized by an excessive immune response. Given the mechanism of action of atezolizumab, SIA is considered a potential risk. SIA should be included in the differential diagnosis for patients who develop a sepsis-like syndrome after administration of atezolizumab. Initial workup should include serum ferritin, CBC, liver function tests, serum triglycerides, and a coagulation profile. In the event of suspected SIA, the Medical Monitor should be contacted for additional recommendations. Treatment with agents such as tocilizumab, as well as corticosteroids, should be considered in the event of SIA.

Potential Pancreatic Toxicity

Symptoms of abdominal pain associated with elevations of amylase and lipase, suggestive of pancreatitis, have been associated with the administration of other immunomodulatory agents.

The differential diagnosis of acute abdominal pain should include pancreatitis. Appropriate assessments should include an evaluation for obstruction, as well as serum amylase and lipase tests. If immune-related pancreatic toxicity is suspected, IgG4 levels and auto-antibodies (anti-plasminogen-binding protein peptide antibodies, peripheral anti-neutrophil cytoplasmic antibodies, anti-mitochondrial antibody, anti-lactoferrin antibody, anti-carbonic anhydrase II, anti-smooth muscle antibody, and anti-nuclear antibody) should be evaluated.

Pericardial Effusions

Pericardial involvement with associated effusions is common in patients with NSCLC and has the theoretical potential to be exacerbated by inflammation associated with anti-tumor immunity following PD-L1 blockade.

Patients presenting with dyspnea, chest pain, or unexplained tachycardia should be evaluated for the presence of a pericardial effusion. Patients with preexisting pericardial effusion should be followed closely for pericardial fluid volume measurements and impact on cardiac function. When intervention is required for pericardial effusions, appropriate assessments include evaluations of cytology, LDH, glucose, cholesterol, and cell count. For patients with a pericardial effusion causing end-diastolic right ventricular collapse, treatment may be restarted following the placement of a pericardial window, demonstration of hemodynamic stability, and resolution of right ventricular dysfunction.

Potential Eye Toxicity

An ophthalmologist should evaluate visual complaints by examination. Uveitis or episcleritis may be treated with topical corticosteroid eye drops. Patients in the study are encouraged to maintain eye hydration, generally through the use of moisturizing eye drops. Atezolizumab should be permanently discontinued for immune-mediated ocular disease that is unresponsive to local immunosuppressive therapy.

Infusion-Related Reactions

With single-agent atezolizumab, IRR symptoms during the infusion have included fever, chills, dyspnea, and flushing/hypotension. They may occur within 30 minutes to 24 hours after infusion, are generally mild and manageable, and wane with subsequent infusions. The most common symptoms reported within 24 hours of the first cycle were pyrexia, fatigue, nausea, hypertension, headache, and diarrhea. IRRs have been reported during Cycles 1 and 2.

Guidelines for Management of Toxicities

| Event | Action To Be Taken |
|---|---|
| General guidance for treatment delays and discontinuation | 
 Permanently discontinue study treatment if any of the following events occur: 
 Grade ≥ 3 non-immune-related adverse event that is considered to be related to study treatment and does not resolve to Grade ≤ 2 within 21 days Non-immune-related adverse event that is considered to be treatment related and requires study treatment to be withheld for > 21 days Immune-related adverse event that requires atezolizumab to be withheld for > 42 days |
| IRRs and anaphylaxis | 
 Guidelines for the management of IRRs are provided above for atezolizumab. In case of anaphylaxis, study treatment should be permanently discontinued. |

CT=computed tomography; FL=follicular lymphoma; G-CSF=granulocyte colony-stimulating factor; IRR=infusion-related reaction; LMWH=low-molecular-weight heparin; NCI CTCAE = National Cancer Institute Common Terminology Criteria for Adverse Events; NHL = non-Hodgkin's lymphoma; NSAID=nonsteroidal anti-inflammatory drug; TLS=tumor lysis syndrome; TSH=thyroid-stimulating hormone; ULN=upper limit normal.

^a Dose modifications apply only to events that are considered to be related to lenalidomide.

^b According to Cairo-Bishop classification system.

^c Graded according to NCI CTCAE Version 3.0.

Guidelines for Management of Toxicities (cont.)

| Event | Action To Be Taken |
|---|---|
| AST, ALT, or bilirubin increase Grade3 (or $\geq 10 \times$ ULN for patients with liver involvement) | 
Withhold study treatment and monitor liver enzymes at least every 7 days.
 
Investigate etiology. Consult with a hepatologist if immune etiology is suspected.
 
 ▪ Corticosteroid treatment may be required for immune-related hepatitis ▪ If there is improvement to Grade 1, resume atezolizumab at full dose. 
Note: If hepatitis is treated with corticosteroids, atezolizumab should not be resumed until the corticosteroids have been tapered to ≤ 10 mg/day of prednisone or equivalent
 
 ▪ Permanently discontinue study treatment for life-threatening liver toxicity |
| Amylase or lipase increase: Grade3 | 
 ▪ Withhold study treatment. 
Investigate etiology. Consult with a gastroenterologist if immune etiology is suspected.
 
Corticosteroid treatment may be required for immune-related pancreatitis
 
 ▪ If there is improvement to Grade 1 and patient is asymptomatic, resume atezolizumab at full dose and resume lenalidomide at current dose. 
Note: If pancreatitis is treated with corticosteroids, atezolizumab should not be resumed until the corticosteroids have been tapered to ≤ 10 mg/day of prednisone or equivalent.
 |
| Ocular toxicity Grade2 (autoimmune uveitis, iritis, or episcleritis) | 
 ▪ Withhold study treatment. ▪ Investigate etiology. Consult with an ophthalmologist. ▪ If there is improvement to Grade 1, resume atezolizumab at full dose. ▪ For immune-related toxicity attributable to atezolizumab, start topical corticosteroid eye drops |

CT=computed tomography; FL=follicular lymphoma; G-CSF=granulocyte colony-stimulating factor; IRR=infusion-related reaction; LMWH=low-molecular-weight heparin; NCI CTCAE=National Cancer Institute Common Terminology Criteria for Adverse Events; NHL=non-Hodgkin's lymphoma; NSAID=nonsteroidal anti-inflammatory drug; TLS=tumor lysis syndrome; TSH=thyroid-stimulating hormone; ULN=upper limit normal. • Dose modifications apply only to events that are considered to be related to lenalidomide.

b According to Cairo-Bishop classification system

c Graded according to NCI CTCAE Version 3.0.

| Event | | Action To Be Taken |
|---|------------------------|--|
| Diarrhea | Grade 4 | 
Permanently discontinue study treatment.
 
 ■ Corticosteroid treatment is suggested for colitis manifested as Grade 4 diarrhea. |
| | Grade 2 or 3 | 
Withhold study treatment.
 
Investigate etiology. Consult with a gastroenterologist if immune etiology is suspected.
 
 ■ Corticosteroid treatment may be required for colitis manifested as Grade 3 diarrhea. ■ If diarrhea improves to Grade 1, resume obinutuzumab at full dose. ■ If immune-related diarrhea improves to Grade 1 and any colitis has cleared as confirmed by sigmoidoscopy (or colonoscopy, if appropriate) with colonic biopsy, resume atezolizumab at full dose. 
Note: If colitis is treated with corticosteroids, atezolizumab should not be resumed until the corticosteroids have been tapered to 10 mg/day or less prednisone or equivalent.
 |
| Pneumopathy, non-infectious (i.e., dyspnea, hypoxia, pulmonary infiltrates) | | 
 ■ Withhold study treatment. Investigate etiology. Consult with a pulmonologist. ■ If symptoms have resolved and CT lung findings are clear, resume atezolizumab at full dose. |
| Tumor flare reaction | Grade 3-4 ^c | 
 ■ Withhold study treatment. Administer corticosteroids, NSAIDs, and/or narcotic analgesics at investigator's discretion. ■ If there is improvement to Grade 1, resume atezolizumab at full dose. |
| | Grade 1-2 ^c | 
 ■ Continue study treatment. ■ Administer corticosteroids, NSAIDs, and/or narcotic analgesics at investigator's discretion. |

CT=computed tomography; FL=follicular lymphoma; G-CSF=granulocyte colony-stimulating factor; IRR=infusion-related reaction; LMWH=low-molecular-weight heparin; NCI CTCAE = National Cancer Institute Common Terminology Criteria for Adverse Events; NHL = non-Hodgkin's lymphoma; NSAID=nonsteroidal anti-inflammatory drug; TLS=tumor lysis syndrome; TSH=thyroid-stimulating hormone; ULN=upper limit normal. • Dose modifications apply only to events that are considered to be related to lenalidomide.

^b According to Cairo-Bishop classification system

^c Graded according to NCI CTCAE Version 3.0.

22. 9 Appendix 9 **Correlative Studies Work Flow**

Pre-treatment, on-treatment and relapsed biopsies will undergo the same analysis/processing and storage, to be performed at three designated MSKCC sites (Pathology Core, Diagnostic Molecular Pathology [DMP] and Hematologic Oncology Tissue Bank [HOTB])

INTERVENTIONAL RADIOLOGY

3-4 Cores: Formalin (all in one container) going to Pathology for:

- Diagnostic IHC
- Research IHC panel (see antibody panel below)
- DNA and RNA extraction for Lymphotrack test (to be given to DMP lab)
- Nanostring Immune Panel (to be given to DMP lab)
-

4 Cores: RPMI (all in one container) going to Pathology for:

- Diagnostic flow
- Research multiparameter flow cytometry (see antibody panel below)

2 Cores*: **Snap frozen** at HOTB and stored

PHELEBOTOMY

1 Purple Top Tube going to Pathology for clinical and research flow

2 Green Top Tubes going to HOTB for PBMC storage

1 Red Top Tube for HOTB for serum cytokines assay

*The snap frozen samples are optional and should only be taken if they can be safely obtained without any additional risk to the patient.

IHC panel

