1.0 PROTOCOL SUMMARY AND/OR SCHEMA

[figure not shown]
This is a two-arm, parallel, open-label, phase II clinical trial designed to assess the efficacy and safety of atezolizumab alone and of atezolizumab in combination with low-dose local radiotherapy in patients with relapsed or refractory follicular lymphoma.

Fifty patients will be enrolled at an estimated accrual rate of 3 patients per month, and will be randomly assigned to receive atezolizumab alone or atezolizumab and local, low-dose radiotherapy.

See Figure 1 for Study Schema.

Figure 1: Study Schema

Subject Randomly Assigned to Treatment Arms

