3.3.2 Clinical Experience with Atezolizumab

3.3.2.1 Ongoing Clinical Studies

Current studies of ATEZOLIZUMAB include one ongoing Phase Ia monotherapy study, three ongoing combination studies, five Phase II studies, and one Phase III study. Details of all ongoing studies can be found in the ATEZOLIZUMAB Investigator's Brochure.

Phase Ib Study BO29563

A phase 1b study of PD-L1 blockade with atezolizumab in combination with the anti-CD20 monoclonal antibody obinutuzumab in patients with relapsed/refractory follicular lymphoma and diffuse large B-cell lymphoma is ongoing. This combination appears well-tolerated, and significant clinical activity has been observed among patients with relapsed/refractory follicular lymphoma, with an ORR of 21.4% (3/14) and CRR of 14.2% (2/14) and 6 additional patients with stable disease at the first response assessment after cycle 4 (Palomba et al. 2016).

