4.2 Intervention

All patients will receive open-label atezolizumab 1200mg IV on day 1 (+/- 2 days) of a 21-day cycle for 1 year, for a planned total of up to 17 cycles of therapy. For patients assigned to receive atezolizumab and low-dose radiotherapy, 4Gy will be administered in 2 fractions to a single nodal site amenable to radiation as identified by the radiation oncologist on day 2 and day 3 of Cycle 1.

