9.2.2 Excluded Therapy

Any concomitant therapy intended for the treatment of cancer, whether health authority approved or experimental, is prohibited. This includes but is not limited to the following:

G-CSF solely to maintain the ANC and not associated with the treatment of a documented or suspected infection in the setting of febrile neutropenia

Chemotherapy, hormonal therapy, immunotherapy, radiotherapy, investigational agents, or herbal therapy

Traditional herbal medicines should not be administered because the ingredients of many herbal medicines are not fully studied and their use may result in unanticipated drug-drug interactions (DDIs) that may cause or confound assessment of toxicity.

The following therapies are excluded while patients are receiving atezolizumab and for 10 weeks after the last dose of atezolizumab:

Patients who are receiving a RANKL inhibitor (denosumab) prior to enrollment must be willing and eligible to receive a bisphosphonate instead; denosumab could potentially alter the activity and the safety of atezolizumab.

Patients are not allowed to receive immunostimulatory agents, including but not limited to IFN- α , IFN- γ , or IL-2. These agents, in combination with atezolizumab, could potentially increase the risk for autoimmune conditions.

Patients should not receive other immunostimulatory agents for 10 weeks after the last dose of atezolizumab.

Patients should not receive immunosuppressive medications, including but not limited to cyclophosphamide, azathioprine, and methotrexate. These agents could potentially alter the activity and the safety of atezolizumab. Systemic corticosteroids and anti TNF agents may attenuate potential beneficial immunologic effects of treatment with atezolizumab but may be administered at the discretion of the treating physician. If feasible, alternatives to these agents should be considered.

Patients must not receive live, attenuated influenza vaccine (e.g., FluMist[®]) within 4 weeks prior to Cycle 1, Day 1 or at any time during the study. Inactivated vaccines are allowed.

In addition, the investigator should contact the Medical Monitor if questions arise regarding medications not listed above.

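### Appendix 8 names two drugs that are not in this trial, leaves one diarrhea branch with no atezolizumab restart line, and conflicts with other sections on endoscopy and hold limits

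*Combined protocol and SAP*

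**What the plan says.** Section 1.0 states that patients are "randomly assigned to receive atezolizumab alone or atezolizumab and local, low-dose radiotherapy". Section 4.2 adds: "All patients will receive open-label atezolizumab 1200mg IV on day 1 (+/- 2 days) of a 21-day cycle for 1 year". Section 9.2.2 closes the door on other anticancer drugs: "Any concomitant therapy intended for the treatment of cancer, whether health authority approved or experimental, is prohibited". Outside Appendix 8, obinutuzumab and lenalidomide appear only as background or as a benchmark. Section 3.3.2.1, for example, describes "A phase 1b study of PD-L1 blockade with atezolizumab in combination with the anti-CD20 monoclonal antibody obinutuzumab", which is a different study.

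The table of management guidelines in Appendix 8 nevertheless contains three references to these drugs:

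- Diarrhea, Grade 2 or 3: "If diarrhea improves to Grade 1, resume obinutuzumab at full dose". The next line covers atezolizumab but opens with a restriction: "If immune-related diarrhea improves to Grade 1 and any colitis has cleared as confirmed by sigmoidoscopy (or colonoscopy, if appropriate) with colonic biopsy".
- Amylase or lipase increase, Grade 3: "resume atezolizumab at full dose and resume lenalidomide at current dose".
- Table legend, repeated under successive parts of the table: "Dose modifications apply only to events that are considered to be related to lenalidomide".

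The closing appendix, on management of atezolizumab adverse events, has its own diarrhea table (Table 3) and its own limit on how long treatment may be held. It carries the label Appendix 1, as does the study flowchart, and it is not in the Section 20 list of appendices.

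**The concern.** A hold-and-resume table should tell a site what to do with the drug the patient is taking. In the Grade 2-3 diarrhea row, study treatment is withheld whatever the cause. The general restart line then names a drug nobody receives, and the atezolizumab line covers immune-related diarrhea only. Simply striking out the wrong drug would leave nothing in Appendix 8 for the non-immune case.

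The same table requires permanent discontinuation when a treatment-related, non-immune event keeps treatment on hold for more than 21 days. A patient with no stated restart rule could therefore be on that clock. Other sections give different answers on endoscopy and on the length of hold, so two investigators could manage the same patient differently, each following the protocol. What is at stake is patient safety and consistent conduct.

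**Working it through.** The documents state no figure to reproduce. The check sets the text side by side and adds one small calculation for scale.

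**Step 1: which Appendix 8 rows are affected.**

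| Row | Drug named for restart | Usable for atezolizumab? |
|---|---|---|
| AST, ALT or bilirubin | Atezolizumab | Yes |
| Amylase or lipase, Grade 3 | Atezolizumab and lenalidomide | Yes; the lenalidomide clause has no patient to apply to |
| Ocular, Grade 2 | Atezolizumab | Yes |
| Diarrhea, Grade 2 or 3, immune-related | Atezolizumab, once any colitis has cleared on endoscopy with biopsy | Yes |
| Diarrhea, Grade 2 or 3, not immune-related | Obinutuzumab only | No |
| Non-infectious pneumopathy | Atezolizumab | Yes |
| Tumor flare, Grade 3-4 | Atezolizumab | Yes |

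Two rows name a non-trial drug. Only one branch of one row is left without an atezolizumab instruction.

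**Step 2: does other text fill the gap?** Table 3 of the closing appendix covers diarrhea or colitis. For both Grade 2 and Grade 3 it allows atezolizumab to resume at Grade 1 or better, subject to a steroid taper if steroids were started. The rows are not limited to immune-related events. Endoscopy and biopsy appear there as steps to establish the diagnosis; the restart line does not require proof that colitis has cleared. So a restart instruction exists, but it does not match Appendix 8 on endoscopic confirmation.

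**Step 3: hold limits before discontinuation.**

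| Source | Limit | Counted from |
|---|---|---|
| Appendix 8, general guidance | 21 days, non-immune and treatment-related; 42 days, immune-related | Not stated |
| Section 9.3 | 42 days, drug-related toxicity; longer for a steroid taper | Scheduled infusion date |
| Closing appendix | 12 weeks (12 x 7 = 84 days); longer for a steroid taper or with Medical Monitor agreement | Event onset |

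Take a treatment-related, non-immune event with no steroid taper. A hold of more than 21 and up to 42 days means discontinuation under Appendix 8 but not under Section 9.3. A hold of more than 42 days beyond the scheduled infusion, still within 84 days of onset, means discontinuation under Section 9.3 but not under the closing appendix. I found no statement of which source takes precedence. Section 11.2.2 adds another source by sending gastrointestinal toxicity to the Investigator's Brochure.

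**Step 4: scale.** Inputs are from Table 1 in Section 3.3.2.2 (558 patients on atezolizumab alone) and 25 patients per arm from Section 14.1.

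- Any grade: 110/558 = 19.7%; 0.197 x 25 = 4.9 per arm.
- Grade 3: 2/558 = 0.4%; 0.004 x 25 = 0.1 per arm.
- Grade 2: not given.

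The expected number with Grade 2-3 diarrhea therefore lies between about 0.1 and 4.9 per arm. The share that is not immune-related is not given either, so 4.9 is a loose upper bound for the branch with the gap.

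**The case against.** The strongest case on the other side is that this is leftover template text that no competent site would follow. Much of that stands. Most of the table works for atezolizumab, and Table 3 of the closing appendix supplies a restart line. It is also unclear that Appendix 8 governs at all: in the text supplied it is named only in the appendix list and its own heading, while Sections 5.1.2 and 11.2.2 send the reader elsewhere.

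A reader might infer that the lenalidomide footnote switches off every rule in the table. The documents do not support that. Where its letter survives, it is footnote a, and no row in the extracted text carries that letter; footnote c, by contrast, is attached to the tumor flare rows. It may be an orphan, or its anchor may have been lost in extraction. It also speaks of dose modifications, which Section 9.3 and the closing appendix treat separately from interruptions.

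A reader might also infer that sites have no restart rule anywhere, or that the choice between arms is affected. The first is contradicted by Table 3. The second is not shown: both arms use the same text, Section 14.4 summarizes adverse events rather than holds or endoscopies, and under Section 14.1 toxicity is weighed only if both arms succeed and the one with more responses is also the more toxic.

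What the objection does not remove is the wrong drug name in an operative line, the missing atezolizumab instruction beside it, and the conflict with the other sections. Common sense tells a site that obinutuzumab is a mistake. It does not tell the site whether atezolizumab was meant in its place, or which hold limit applies.

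**Conclusion.** Wrong as written, in a limited way. Two Appendix 8 rows and one footnote refer to drugs outside the trial. One branch, non-immune Grade 2-3 diarrhea, has no atezolizumab restart instruction in that appendix. The instruction in the closing appendix differs on endoscopic confirmation, and the hold limits conflict across Appendix 8, Section 9.3 and the closing appendix.

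The number of patients is small to moderate and cannot be pinned down: the scale in Step 4 assumes that rates from the earlier single-agent study carry over to this population, and Grade 2 counts are missing. The reading of Table 3 rests on its rows being unrestricted by cause, although the paragraph introducing them speaks of immune-related colitis.

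This is a patient-safety and conduct point. It does not touch the sample size, the error rates or the primary analysis.

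**What to change.** Correct the obinutuzumab and lenalidomide references in the Appendix 8 table, and the lenalidomide footnote wherever it is repeated. Reconcile the Appendix 8 diarrhea row with Table 3 of the closing appendix, including whether endoscopic confirmation is a condition of restart and what applies when diarrhea is not immune-related. Reconcile the hold limits in Appendix 8, Section 9.3 and the closing appendix, including the date from which each is counted, so that one rule applies. Which rule that is, and whether a drug name should be removed or replaced, is for the sponsor's clinicians.

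The cost is protocol wording only. No statistical parameter changes.
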